Official title:

**EFFECT OF A NUTRIGENETIC INTERVENTION ON BLOOD LIPID MARKERS AND BODY
COMPOSITION OF ADULTS WITH OVERWEIGHT AND OBESITY**

STUDY PROTOCOL

September, 30, 2021

“EFFECT OF A NUTRIGENETIC INTERVENTION ON BLOOD LIPID MARKERS AND BODY COMPOSITION IN OVERWEIGHT AND OBESO ADULTS”

STUDY PROTOCOL

- **Hypothesis**

A nutrigenetic diet administered to adults with genetic polymorphisms related to obesity and dyslipidemias will provide a greater decrease in plasma lipids, inflammatory markers and improvement in body composition, compared to the administration of a standard diet.

- **Objective:**

To evaluate the effect of a nutrigenetic intervention on blood biochemical and inflammatory markers and body composition in overweight and obese adults.

- **Design:**

Study type: Interventional

- **Interventional Study Model:**

Randomized controlled clinical trial, parallel assignment, with 2 study groups.

Two arms.

Masking: Single (participant).

Intervention period: 8 weeks.

Research site: ITESO and Centro Universitario de Ciencias de la Salud, Universidad de Guadalajara, México.

- **Methods:**

Participants

The recruitment of the population was carried out from the month of May to the month of September of the current year in the CD of Guadalajara, Jalisco and neighboring municipalities. The dissemination of informative flyers was done digitally through various social networks and also verbally.

Inclusion criteria

-Men and women

-18-50 years old

-Mexican- mexican ancestry (3 generations at least)

-Live in Guadalajara, Jalisco or metropolitan area

-Being overweight or obese (BMI 25>40)

-Waist circumference:

Women: > 80 cm

Men: > 94 cm

-Availability to attend virtual nutritional consultations.

Exclusion criteria

- Not meeting the inclusion criteria
- Pregnancy or breastfeeding
- Gastrointestinal disorders
- Endocrinopathies
- Cardiovascular events
- Diagnosed psychiatric illnesses
- Diagnosed diabetes
- Take lipid-lowering drugs
- Autoimmune diseases
- Covid +

Dependent variables:

Height, body weight, BMI, total body fat, fat mass index, skeletal muscle mass, visceral fat, waist circumference, hip circumference, total cholesterol (TC), LDL-cholesterol (LDL-C), HDL-cholesterol (HDL-C), triglycerides, C-reactive protein (CRP), glucose and insulin, total energy, macronutrients, micronutrients.

Independent variables:

Sex, age, presence or absence of polymorphisms, and intervention group.

INTERVENTION

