Official title:

**EFFECT OF A NUTRIGENETIC INTERVENTION ON BLOOD LIPID MARKERS AND BODY
COMPOSITION OF ADULTS WITH OVERWEIGHT AND OBESITY**

STATISTICAL ANALYSIS PLAN

September , 30, 2021.

Statistical analysis plan

Sample size was calculated *a priori*, considering the mean difference in total cholesterol between study groups as primary outcome variable (De Luis et al. 2017). GPower V3.1.9.4 software was used for the pertinent calculations. A power contemplated: 95%, and significance α : 0.5%. The effect size: 0.9772364. One-tailed, to analyze differences with the t-test. 30% loss to follow-up was considered. A minimum of 24 participants per treatment were required. The aim was to recruit 50 subjects per treatment

All the data will be analyzed using SPSS for MAC, version 26.0 software package (SPSS Inc. Chicago, IL). Parametric tests will be applied for quantitative variables with normal distribution, and non-parametric tests for qualitative and quantitative variables with abnormal distributions. The Kolmogorov–Smirnov test will be used to determine variable distribution. The results will be expressed as average \pm standard deviation.

For each treatment group, all markers will be tested using Student's paired-sample t test for possible difference between values achieved at baseline (visit 1) and 1st month (4 weeks) and visit 3 (final point, 8 weeks), respectively. Student's two independent- samples t tests will be also performed to find possible difference regarding these markers between treatments Nutrigenetic diet and Conventional diet. Furthermore, a mixed models approach including repeated-measures modeling will be utilized to find possible significant effects of the treatment effect at baseline on treatment effect after two subsequent clinical visits. This model will considerate confounders.

Categorical variables will be analyzed with the chi-square test, with Yates correction as necessary, and Fisher's test.

The statistical analysis to evaluate the gene-diet interaction was a univariate ANCOVA.

A Chi square test will be used to evaluate the Hardy–Weinberg equilibrium.

A P- value b 0.05 was considered significant.

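### No between-diet analysis of total cholesterol is committed to adjusting for baseline or the randomisation strata, and none is named as primary: a cheap loss of precision, not a bias

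*SAP*

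**What the plan says.** The sample-size paragraph of the SAP sets the target by "considering the mean difference in total cholesterol between study groups as primary outcome variable", and the test by "One-tailed, to analyze differences with the t-test". It also says "30% loss to follow-up was considered", gives a minimum of 24 per treatment and aims to recruit 50.

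The treatment-comparison paragraph plans paired t-tests within each diet, from baseline to week 4 and to week 8. For the comparison between diets it says "independent- samples t tests will be also performed to find possible difference regarding these markers between treatments". It does not say which visit decides, or whether values or changes are compared, although it does call week 8 the final point.

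A repeated-measures mixed model is then added, to look for "significant effects of the treatment effect at baseline on treatment effect after two subsequent clinical visits". On covariates it says only "This model will considerate confounders". ANCOVA appears once, for the gene-diet interaction.

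In the protocol, the Randomization section stratifies allocation by age, BMI and sex. The Biochemical measurements section collects total cholesterol at baseline, week 4 and week 8. The list of independent variables reads "Sex, age, presence or absence of polymorphisms, and intervention group". It contains neither BMI nor a baseline value and is not tied to any model.

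**The concern.** The test used for the sample size and the test first named for comparing diets are the same unadjusted t-test. By implication, though not by declaration, that is the main analysis. It has no term for the stratification factors, and it uses baseline cholesterol only if it is run on changes.

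Baseline cholesterol will be in hand for everyone randomised and is likely to predict the week-8 value. Leaving it out widens the confidence interval for no saving. Leaving the visit, the scale, the model form and the covariates open also means that several different analyses fit the text, and the choice could be made after the data are seen.

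**Working it through.** **Inputs from the documents.** Effect size 0.9772364, one-tailed, power 95%, minimum 24 per arm, target 50 per arm, 30% loss, 1:1 allocation. Evaluable per arm: 50 × (1 − 0.30) = 35.

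**Assumptions not in the documents.** Correlation r between baseline and week-8 cholesterol of 0.3 to 0.8 (0.2 also tried); equal SDs at both visits; effect sizes in units of the week-8 SD; alpha 5%; an illustrative smaller effect of 0.5 SD; age, BMI and sex explain nothing beyond baseline.

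**The plan's own figure.** For a two-sample t-test, power comes from the noncentral t with 2n − 2 degrees of freedom and noncentrality d√(n/2). With d = 0.9772364, one-sided alpha 5%:
- n = 23 gives 94.7%.
- n = 24 gives 95.4%.

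So 24 per arm is the evaluable number for an unadjusted t-test. The printed alpha of 0.5% would need 40 per arm; that mismatch is a separate matter.

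**Variance of the estimated diet difference** (σ = SD of cholesterol):
- Week-8 values: 2σ²/n.
- Changes: (2σ²/n) × 2(1 − r).
- Baseline-adjusted (ANCOVA): (2σ²/n) × (1 − r²).

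Adjusted over week-8 values is 1 − r²: 0.91 at r = 0.3 and 0.36 at r = 0.8, a cut of 9% to 64%. Adjusted over changes is (1 + r)/2: 0.65 and 0.90, a cut of 35% to 10%.

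**Cost of adjusting.** Four covariates (baseline cholesterol, age, BMI, sex) use four degrees of freedom, 70 − 2 − 4 = 64. Chance imbalance multiplies the variance by about 1 + 4/(70 − 7) = 1.063. This ignores the balance that stratification brings, so it is on the harsh side for the adjusted analysis.

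**35 per arm, 0.5 SD, two-sided 5%** (95% CI half-width in SD in brackets):

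| r | Week-8 values | Changes | Adjusted, after cost |
|---|---|---|---|
| 0.2 | 54% (0.48) | 37% (0.60) | 53% (0.48) |
| 0.3 | 54% (0.48) | 41% (0.56) | 55% (0.47) |
| 0.5 | 54% (0.48) | 54% (0.48) | 64% (0.43) |
| 0.8 | 54% (0.48) | 90% (0.30) | 91% (0.30) |

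On the SAP's one-tailed basis the same 0.5 SD gives 66% on week-8 values, 54% to 95% on changes and 68% to 96% adjusted, for r = 0.3 to 0.8. The ordering is unchanged.

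**35 per arm, planned 0.977 SD, one-sided, r = 0.3:** 99.2% on week-8 values, 96.2% on changes, 99.3% adjusted after cost.

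**Where the gain vanishes.** At r = 0.2 with 35 per arm, 0.5 SD two-sided: 53.2% adjusted against 54.1% on week-8 values. At r = 0.3 with only 24 per arm: 39.5% against 39.6%.

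**Ignoring the strata.** In a simulation of 24 per arm balanced within eight assumed strata, the two-sided 5% t-test had a true type I error of 4.9%, 4.0%, 2.8% and 1.9% when strata explained 0%, 10%, 20% and 30% of the variance. The unadjusted test errs on the conservative side.

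**The case against.** The strongest reply is that an adjusted longitudinal analysis is already planned. The mixed model refers to baseline and to confounders, week 8 is called the final point, and the candidate covariates are visible in the protocol: age and sex among the independent variables, and age, BMI and sex as stratifiers. If the model is meant to carry baseline as a covariate with a week-8 contrast, nothing is gained by asking for it. This stands in part. It makes the point one of commitment as much as of method, because the text never makes that model or that contrast the deciding analysis and never links a covariate to it.

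It also stands that the gain is small at the trial's own planned effect, that the larger gains need an effect and a correlation the documents do not give, and that the benefit of adjusting for the strata themselves has not been quantified.

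A reader might infer several stronger things that the documents do not support:
- **That the t-test biases the comparison or inflates false positives.** Allocation is randomised, and ignoring the strata is conservative.
- **That the mixed model would average the diet effect over all three visits and dilute it.** The SAP sets baseline apart from the two later visits and mentions no average.
- **That adjustment always does at least as well as the better t-test.** It does not at very low correlation, or with few evaluable participants.

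**Conclusion.** The point holds as a cheap improvement. No between-diet analysis of the primary outcome is committed to baseline cholesterol or to the stratification factors, and no analysis is declared primary.

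Its size depends on the unknown correlation. Over r = 0.3 to 0.8 with 35 per arm, adjustment tracks or beats whichever t-test scale turns out better, whereas fixing on values or on changes risks the worse one: 54% against 90% power at r = 0.8, or 41% against 54% at r = 0.3. The advantage over the better scale is about 1 percentage point at either end of that range and about 10 in the middle.

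The power gain matters only if the true effect is well below the planned one. Confidence is medium, because the intended mixed model may already be close to what is recommended.

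**What to change.** Declare as primary the week-8 difference between diets in total cholesterol, with its confidence interval, from the planned repeated-measures mixed model. Weeks 4 and 8 are the outcomes. The fixed effects are arm, visit, arm-by-visit, baseline total cholesterol, age, baseline BMI and sex. An ANCOVA of the week-8 value with the same covariates is an acceptable equivalent.

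Replace the general reference to confounders with that list. State that no variable measured after randomisation (weight change, intake or physical activity during the diet) enters the model. Keep the t-tests as supportive, with their visit and scale stated.

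The cost is a few lines of SAP text. The model can be fitted in the SPSS version already named, and no new data or visits are needed. The downside is a few degrees of freedom, and slightly less precision than week-8 values alone if the correlation proves very low.

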All the subjects will give their written informed consent before inclusion in the study. The present study was approved by the ethical committee for human research of Instituto Tecnológico y de Estudios Superiores de Occidente (ITESO) (0001DRC) and was performed in accordance with the ethical standards laid down in the 1964 Declaration of Helsinki and its later amendments.

Randomization:

Participants will be randomly assigned, using a computerized random number generator (STATA software), to one of two treatments: nutrigenetic diet or conventional diet. Randomization will be stratified according to age, BMI and sex. The allocation ratio will be 1:1

Genotyping of gene polymorphisms related to dyslipidemias in Mexicans

Based on a previous systematic review, 11 gene polymorphisms associated with dyslipidemias in Mexicans were identified and were taken into account to perform genotyping in the study population.

The gene polymorphisms under study are:

ABCA1 rs9282541

PPARG rs1801282
LIPC rs1800588
CETP rs708272
LPL rs13702
FABP2 rs1799883
APOA5 rs662799
APOC3 rs5128
APOA1 rs670
APOE rs429358 and rs7412

A blood sample will be taken from the participants, then DNA will be extracted from leucocytes using a commercial extraction kit (High Pure PCR Template Preparation kit, *Roche*). Polymorphisms will be detected by a real-time RT-PCR system using allelic discrimination (TaqMan ®) in a 96-well format and will be read by a Roche LightCycler 96 system (Roche, Mannheim, Germany). PCR conditions will 40 cycles of amplification at 95°C for 10 min, and annealing/ extension at 60°C for 60 seconds.

The experimental phase will last 8 weeks.

Participants will attend 3 three visits to the clinical unit (Centro Universitario de Ciencias de la Salud, Universidad de Guadalajara): on the starting day of the intervention period (baseline), after 4 weeks (1st month) and after 8 weeks of intervention (final visit). Participants will also receive remote nutritional counseling every 15 days (5 consultations in total).

Anthropometric measurements

Anthropometric parameters will be measured three times during intervention period (baseline, week 4, week 8).

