Measurements will be performed after 8- 10 hours of fasting. Height measurements will be taken using a stadiometer (Rochester Clinical Research, Rochester, NY, USA). Tetrapolar electrical bioimpedance will be used to assess weight and body composition (InBody 120 body composition analyser; Biospace, Seoul, Korea). BMI will be calculated as weight in kilograms divided by height in meters squared (kg/m²). The waist (narrowest diameter between the xiphoid process and the iliac crest) and hip (the widest diameter over the greater trochanters) circumferences will be measured (Lufkin anthropometric tape W606PM). Blood pressure will be measured, while seated, in the non- dominant arm using a digital automatic BP monitor (Model M3 Intelligence, Omron, Healthcare Company, Limited).

Biochemical measurements

Biochemical measurements will be performed three times during intervention period (baseline, week 4, week 8).

Venous blood samples will be taken after overnight fasting, and serum will be immediately separated by centrifugation. Measurements of total cholesterol, triglycerides, high-density lipoprotein cholesterol (HDL-C), glucose, very low density lipoprotein (VLDL) and C- reactive

protein will be performed using a Vitros-250 dry chemistry analyser (Ortho- Clinical Diagnostics, Johnson & Johnson Services, Inc., Rochester, NY, USA). LDL-C levels will be calculated using the Friedewald formula. The homeostatic model assessment of insulin resistance (HOMA-IR) will be calculated as described by Matthews et al. (1985). Insulin levels will be determined by an Immunoassay Kit (LIAISON®).

The inflammation markers IL-1, IL-6, IL-10 and TNF- α , will be determined using ProQuantum High-Sensitivity Immunoassays technique

Diets

As above-mentioned, patients will be randomly allocated to one of two diets for a period of 8 weeks.

NUTRIGENETIC DIET: Weekly, personalized meal plans (menus) will be provided every 2 weeks, prepared based on the anthropometric needs of the patients, with a caloric reduction (-500 kcal). These weekly menus (Sunday to Monday) consist of 5 meal times (breakfast, snack, lunch, snack and dinner). The distribution of the macronutrients: carbohydrates, proteins and fats, as well as the percentages of polyunsaturated, monounsaturated and saturated fatty acids, will be established according to certain nutrigenetic recommendations identified in the reference bibliography.

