CONVENTIONAL DIET: weekly, personalized meal plans (menus) will be provided every 2 weeks, prepared based on the anthropometric needs of the patients, with a caloric reduction (-500 kcal). These weekly menus (Sunday to Monday) consist of 5 meal times (breakfast, snack, lunch, snack and dinner). The target macronutrient composition of this treatment is: 50% carbohydrates, 20% proteins and 30% fats in accordance with the recommendations made by the WHO (World Health Organization), the AHA (American heart association) and the NOM (Official Mexican Standards) for the treatment of obesity and dyslipidemias.

The percentages of macronutrients and fatty acids of all the menus will be adjusted using Foodprocessor nutrition software ®

All participants will receive remote (virtual) nutritional counseling every 15 days (5 individual sessions) with the dietitian to explain the diet, solve doubts, provide nutrition strategies and to complete the nutritional medical history, which includes physical activity record (IPAQ- short version) and questionnaires of frequency of food consumption to monitor adherence to nutritional intervention. Records will be analyzed with a computer-based data evaluation system (Foodprocessor nutrition software ®). National composition food tables will be also used as reference.

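### Gene-diet interaction is tested by ANCOVA at a flat 0.05 with 11 variants and no multiplicity control, and a genotype-by-arm term would not isolate that interaction if menus follow genotype

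*SAP*

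**What the plan says.** The SAP's only text on this analysis is "The statistical analysis to evaluate the gene-diet interaction was a univariate ANCOVA". It names no outcome, time point, genetic coding, covariates or interaction term, and does not say whether diet means assigned arm or measured intake. The one decision rule, for every test, is "A P- value b 0.05 was considered significant" (the letter b evidently stands for a less-than sign). No multiplicity adjustment, test hierarchy or exploratory label appears.

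The protocol supplies the rest of the picture:

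- **Variants** (genotyping section): "11 gene polymorphisms associated with dyslipidemias in Mexicans were identified". The list that follows has nine single-SNP entries and one APOE entry with two SNPs.
- **Independent variables** (Methods): besides sex and age, "presence or absence of polymorphisms, and intervention group". Energy and macronutrients are listed among the dependent variables.
- **Conventional diet** (Diets): one target for everyone, "50% carbohydrates, 20% proteins and 30% fats".
- **Nutrigenetic diet** (Diets): macronutrient and fatty-acid composition "will be established according to certain nutrigenetic recommendations identified in the reference bibliography". No fixed target and no rule from genotype to composition is printed.

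**The concern.** There are two problems, and the first does not depend on the second.

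**Multiplicity.** Eleven variants examined one at a time at 0.05 give a substantial chance of a nominally significant interaction when none exists.

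**Interpretation.** The protocol classes intake as an outcome, so the only diet factor among its independent variables is the arm. Genotype by arm is therefore the natural model. In the conventional arm all genotypes have the same target composition. If composition in the nutrigenetic arm follows genotype, carriers and non-carriers there eat different menus. The product term then compares different diets across genotypes as well as different responses to the same diet. It can be non-zero when every genotype responds identically to any given diet.

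At stake is a secondary but prominent conclusion. A significant product term could be reported as gene-diet interaction when it shows only that two menus differ, or when it is one chance result among eleven.

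**Working it through.** **Inputs from the documents.** 11 variants, or 10 loci with the APOE SNPs combined; 0.05 per test; 1:1 allocation; minimum 24 per arm; 30% loss; target 50 per arm; planning effect 0.9772364.

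**Plan's own figure.** No sample size or power is given for the gene-diet ANCOVA. The 24 per arm for the total cholesterol t-test reproduces at one-sided alpha 5% and 95% power (noncentral t: n = 24, power 95.4%). It does not reproduce at the printed "significance α : 0.5" per cent, which needs 40 per arm one-sided. The 24 is before dropout: 24/0.7 = 34.3, so 35 per arm. I use 35 and 50 as the plausible sizes.

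**Step 1: family-wise error, one outcome, independent tests.** Formula: 1 − (1 − 0.05)^k.

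- k = 11: 1 − 0.5688 = 43.1%
- k = 10: 1 − 0.5987 = 40.1%

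Linked variants lower these figures; more outcomes or visits raise them. The first Holm threshold would be 0.05/11 = 0.0045, or 0.05/10 = 0.005 for 10 loci.

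**Step 2: rejection by the genotype-by-arm term with no biological interaction.** Assumptions, none of them in the documents: residual SD 1; carrier share f between 20% and 50%, equal in both arms; genotype and diet effects purely additive; in the nutrigenetic arm the carriers' menu shifts the outcome by δ SD relative to the non-carriers' menu; two-sided 5% test.

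The product term then has expectation δ and standard error √[2/(n f (1 − f))] for n per arm:

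- n = 35, f = 0.2: √(2/5.6) = 0.598
- n = 35, f = 0.5: √(2/8.75) = 0.478
- n = 50, f = 0.2: √(2/8) = 0.500
- n = 50, f = 0.5: √(2/12.5) = 0.400

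Rejection rates from the noncentral t with 2n − 4 degrees of freedom and noncentrality δ/SE:

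| δ (SD) | n = 35, f = 0.2 | n = 35, f = 0.5 | n = 50, f = 0.2 | n = 50, f = 0.5 |
|---|---|---|---|---|
| 0 | 5.0% | 5.0% | 5.0% | 5.0% |
| 0.2 | 6.3% | 7.0% | 6.8% | 7.9% |
| 0.5 | 13.1% | 17.8% | 16.8% | 23.6% |
| 0.8 | 26.1% | 37.8% | 35.4% | 50.8% |

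Simulation at δ = 0.5 (4,000 trials per setting) agrees: 12.8% and 17.0% at 35 per arm, 16.3% and 22.9% at 50.

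**Step 3: no tailoring.** If everyone in the nutrigenetic arm has the same composition, the product term has expectation zero when there is no biological interaction. Simulated rejection was 4.5% to 5.5% at 24, 35 and 50 per arm with 30% or 50% carriers.

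**The case against.** The strongest reply is that much of this is inference.

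- **The model is not written down.** The list of independent variables is not a model, and genotype by measured intake is possible because food-frequency data are collected. This stands in part: genotype by arm is the natural reading but not the only one.
- **Tailoring by genotype is not printed.** A reader might infer that genotype sets the diet by design, so that the ANCOVA cannot test gene-diet interaction at all. The documents do not support that. The nutrigenetic recommendations sit in a bibliography, the menus in both arms are individualised to anthropometric needs, and the hypothesis could describe one composition for the whole arm. In that case the term is an ordinary interaction test with 5% error.
- **The rates are power for a real difference.** Under tailoring, the term validly detects that the effect of the assigned strategy differs by genotype. That is correct. The error would lie in what the term is called.
- **The 0.5 and 0.8 SD values have no source.** They are about half and four-fifths of the 0.977 SD planned for the whole arm. If 11 variants jointly shape the menu, the contrast for any one variant may be nearer 0.2 SD, where the excess over 5% is small.
- **The number of tests is not stated.** A reader might infer that all markers are tested for every variant; the SAP does not say so. The 43% needs only one outcome and one test per variant.

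The multiplicity point survives the first four objections. It depends on the fifth only through the assumption of one test per variant.

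**Conclusion.** The concern holds in two parts of unequal certainty.

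The firmer part is error control. With one ANCOVA per variant at 0.05, the family-wise error for a single outcome is about 43% (40% for 10 loci), assuming independence.

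The conditional part is interpretation. If the model is genotype by arm and the nutrigenetic menus follow genotype, the term mixes menu differences with biological interaction. The resulting rejection rate is roughly 13% to 24% at an assumed 0.5 SD menu difference, 6% to 8% at 0.2 SD, and 5% without tailoring. The stronger conclusion, that the analysis cannot address gene-diet interaction, does not follow from what is printed.

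The hypothesis and objective concern nutrigenetic versus standard diet and do not mention interaction. The primary randomised comparison of total cholesterol is untouched. The SAP should still be changed, because the change is cheap and limits what can be claimed from a secondary analysis.

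**What to change.** In the SAP:

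1. Write out the ANCOVA: outcome and visit, genetic coding (including how the two APOE SNPs are handled), covariates, the product term and the meaning of diet. State whether and how genotype determined menu composition, so that a reader can judge the term.
2. Apply Holm or false discovery rate control across the variant tests and label the set exploratory.
3. Report a genotype-by-arm term as modification of the diet-strategy effect by genotype. Where menus were tailored, do not interpret it as gene-diet interaction.
4. Treat any genotype-by-recorded-intake model, adjusted for arm and baseline, as an observational sensitivity analysis only. It is not a clean replacement: intake is self-reported, measured after randomisation, and still partly set by genotype in the nutrigenetic arm if menus were tailored.

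The cost is SAP wording and modest extra analysis of data already planned. The downside is lower power per variant, starting from a low base: read as power, the 0.5 SD row above is only 13% to 24% even at an unadjusted 0.05. The nutrigenetic conclusion also becomes more modest.

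### The SAP names total cholesterol as primary but no deciding visit, scale, model or sidedness; one unadjusted 0.05 rule covers every test, and the printed sizing alpha of 0.5% does not give 24 per arm

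*SAP*

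**What the plan says.** The SAP's sample-size paragraph describes the calculation as "considering the mean difference in total cholesterol between study groups as primary outcome variable". It gives 95% power, an alpha and effect size printed as "0.5%. The effect size: 0.9772364", and the test as "One-tailed, to analyze differences with the t-test". It allows for 30% loss and concludes "A minimum of 24 participants per treatment were required", followed by "The aim was to recruit 50 subjects per treatment".

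The analysis paragraphs then list, without ranking:

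- paired t-tests within each arm ("For each treatment group, all markers will be tested using" these), comparing baseline with week 4 and with "visit 3 (final point, 8 weeks";
- independent-samples t-tests between the two diets on the same markers, with no visit, scale or sidedness;
- a repeated-measures mixed model with unnamed confounders;
- a univariate ANCOVA for gene-diet interaction, with no outcome or number of models.

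The closing sentence covers all of them: "A P- value b 0.05 was considered significant". The b is taken as a less-than sign damaged in print or extraction and is not counted as an error.

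The Protocol lists total cholesterol among its dependent variables and biochemical measurements but designates no primary outcome. Its hypothesis spans plasma lipids, inflammatory markers and body composition.

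**The concern.** Two things are unsettled. First, the primary variable is named but the primary test is not. Week 4 or week 8, attained value or change from baseline, t-test or mixed model, one-sided or two-sided: each combination is consistent with the text. More than one total-cholesterol result could therefore be presented as the primary one. Because nothing is labelled secondary, any other marker can also be called significant at the same threshold. A reader of the results could not separate the confirmatory finding from chance findings.

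Second, the printed sizing alpha of 0.5% disagrees with both the closing 0.05 rule and the 24 per arm, so the sample-size statement is wrong as it stands.

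**Working it through.** **Sample size**

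Inputs, all from the SAP's sample-size paragraph: d = 0.9772364, power 95%, two-sample t-test, one-tailed. The 1:1 allocation is from the Protocol's Randomization text. Power for n per arm is the probability that a noncentral t with 2n − 2 degrees of freedom and noncentrality d·√(n/2) exceeds the critical value.

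Reproducing the plan's figure at one-tailed 5%: n = 24 gives noncentrality 0.9772364 × √12 = 3.385, critical value 1.679 on 46 df, power 95.4%. With n = 23 the power is 94.7%. So 24 is exactly the minimum.

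At the printed one-tailed 0.5%: n = 24 has the same noncentrality but critical value 2.687, giving power 75.4%. The smallest n reaching 95% is 40 (95.6%).

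| Alpha | n per arm for 95% power | Power at 24 | Power at 35 |
|---|---|---|---|
| 0.5% one-tailed (printed) | 40 | 75.4% | 92.1% |
| 5% one-tailed | 24 | 95.4% | 99.2% |
| 5% two-sided | 29 | 91.2% | 98.1% |

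The 35 is the recruitment aim less the SAP's loss: 50 × 0.7.

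Loss allowance: 24/0.7 = 34.3, so 35 recruited if 24 is the evaluable number. If 24 already includes the loss, 24 × 0.7 = 16.8, about 17 completers, with 87% power at one-tailed 5%. For two-sided 5%, 29/0.7 = 41.4, so 42 recruited.

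**Choice of total-cholesterol test**

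Assumptions, not in the documents: no true diet difference, 35 evaluable per arm, normal data, three visits with a common pairwise correlation r. The test statistics for week-8 value and week-8 change then correlate at about √((1 − r)/2): 0.50 at r = 0.5, 0.39 at 0.7 and 0.32 at 0.8. They are far from interchangeable. Simulating 40,000 trials at each r gives these chances of at least one significant result:

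| Free choice | r = 0.5 | r = 0.7 | r = 0.8 |
|---|---|---|---|
| Week 8, value or change, two-sided 0.05 | 9.2% | 9.5% | 9.3% |
| of which favouring the nutrigenetic diet (nominal 2.5%) | 4.5% | 4.6% | 4.6% |
| Week 8, value or change, one-sided 0.05 (nominal 5%) | 8.6% | 9.1% | 9.2% |
| Week 4 or 8, value or change, two-sided 0.05 | 16.4% | 16.0% | 15.7% |

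A repeat run agreed within 0.3 percentage points. Adding a baseline-adjusted week-8 model as a further option raises the first row to about 10%. Any single test, fixed in advance, stays at about 5%.

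**Number of markers**

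The Protocol's dependent variables, without height and dietary intake, give 15: eight body measures (weight, BMI, body fat, fat mass index, muscle mass, visceral fat, waist, hip) and seven blood markers (TC, LDL-C, HDL-C, triglycerides, CRP, glucose, insulin). Biochemical measurements adds VLDL, HOMA-IR, IL-1, IL-6, IL-10 and TNF-α: 15 + 6 = 21. With equally correlated normal statistics, one visit and two-sided 0.05, the chance of at least one false positive is:

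| Markers | Correlation 0.7 | 0.5 | 0.3 |
|---|---|---|---|
| 15 | 26% | 36% | 46% |
| 21 | 29% | 43% | 55% |

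About half of these would favour the nutrigenetic diet: 13% to 23% for 15 markers, 15% to 29% for 21.

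**The case against.** The strongest reply is that the primary question is nearly settled. The SAP gives the outcome, the contrast, the test family and a tail. It calls week 8 the final point, and the Protocol calls it the final visit. On that reading one linking sentence is missing, and the week-8 inflation (9% against 5%) is modest. This is fair: the 16% figure needs week 4 to count as primary, which the documents neither state nor exclude. Even so, final point is a label for a visit, not a designation, and scale, model and sidedness remain open. Many trials also report unadjusted secondary tests, but this SAP labels nothing secondary.

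Four stronger readings are tempting and not supported:

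- *No primary outcome is named, or total cholesterol appears only in the sizing text.* It is named, it is listed in the Protocol, and between-arm t-tests are in the analysis text. Only its primary status and the one-tailed direction are confined to the sizing paragraph.
- *The trial is underpowered, or its sizing alpha is unknowable.* With the printed power, effect size and tail, 5% reproduces 24 exactly. Two-sided 5% at 90% power also gives 24, but contradicts the printed 95% and one-tailed. At 35 evaluable per arm, power is 92% even at one-tailed 0.5%.
- *Diet effects will be claimed from within-arm paired tests.* The SAP does not say so, and it plans between-arm tests. Since both diets cut 500 kcal, a sentence excluding that inference is useful, but its absence is not an error.
- *Error rates computed for independent tests, or for one gene-diet model per polymorphism.* These are upper bounds only. LDL-C, BMI and HOMA-IR are calculated from other measurements, and the SAP does not give the number of gene-diet models.

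**Conclusion.** The point stands at moderate weight: it should be fixed, and the design survives it. Two parts are firm because they rest on the text and the SAP's own inputs: no deciding visit, scale, model or sidedness is specified, and 0.5% one-tailed is incompatible with 24 per arm (40 needed; 75.4% power at 24). That 0.5% is a misprint of 5% is the most likely explanation, not a certainty. The power consequence is small provided 50 per arm are recruited and loss does not exceed 30%.

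The false-positive rates (about 9% for week-8 total cholesterol, about 16% if week 4 counts, 26% to 55% across markers) depend on assumed correlations and on 35 evaluable per arm. The inflation persists over the whole range examined. All power figures take the SAP's effect size as given; its source is not in the documents.

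**What to change.** (a) Check the sizing output and, if it confirms the recalculation, correct 0.5% to 5% one-tailed. State that 24 is the evaluable number, with 35 recruited at 30% loss. If 24 already includes the loss, restate power as about 87% for 17 completers.

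(b) Name one deciding test, for example the between-arm difference in total cholesterol at week 8 from one specified baseline-adjusted model, with its covariates, sidedness and alpha. If two-sided 0.05 is chosen, restate power as 91% at 24 and 98% at 35 evaluable per arm. Reaching 95% then needs 29 evaluable, or 42 recruited, which is within the planned 50.

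(c) Label all other markers, visits and gene-diet models secondary or exploratory, and give the number and outcomes of the gene-diet models. Adjust for multiplicity (Holm or false discovery rate, say) only where significance is still claimed. Report within-arm changes as descriptive estimates with 95% confidence intervals, and base diet conclusions on between-arm contrasts.

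The cost is SAP wording only if one-tailed 5% is kept and 24 is the evaluable number; two-sided 0.05 raises the stated minimum but not the recruitment aim. The downside is that some secondary and interaction results lose nominal significance.
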